#### 2. Length of Stay

2752 patients would enable a Minimum Clinically Significant Difference (MCSD) [between diagnostic policies] of 1 day in the mean length of stay (assuming SD=6 days) to be detected at the 5% significance level with over 80% power, assuming a 20% dropout rate and adjusting for the fact that there are 3 groups.

#### 3. Appropriate Isolation Levels:

2752 patients would also enable a Minimum Clinically Significant Difference (MCSD) [between diagnostic policies] of an improvement in appropriate use of isolation facilities from 5% to 15% to be detected at the 1% significance level with over 95% power, assuming a 20% dropout rate and adjusting for the fact that there are 3 groups.

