#### 7.4 Statistical power

Statistical power has been estimated for one laboratory and two clinical endpoints for the elderly population only.

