  First, the proportion of patients with *S. pneumoniae* infection in Groups 1, 2, and 3.
  Second, to better define the burden of influenza and RSV, the proportion of all patients with (i) influenza, and (ii) RSV, who die.
- 3. Quality of life, as measured by EuroQol, and quality adjusted life years generated during the 28 days after admission, will be assessed:
  - (a) In all patients in Groups 1, and 2 in comparison to Group 3.

- (b) Second, in patients in patients with (i) influenza, (ii) RSV, and (iii) *S. pneumoniae* in Groups 1, and 2, in comparison to Group 3.
- 4. Use of isolation facilities
  - (a) The time from admission to the MAU to the time of admission to a single room (isolation cubicle) will be compared for patients with confirmed influenza or RSV in Groups 1, 2, and 3.
  - (b) The proportion of patients with influenza or RSV in Groups 1, 2, and 3 who are isolated at any stage during the first 120 hours of the admission.
  - (c) The proportion of patients with *S. pneumoniae* infection in Groups 1, 2, and 3 who are inappropriately isolated for >12 hours.

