Admission to intensive care The proportions of patients in the three groups who are admitted to intensive care within the first 10 days of admission will be compared using  $\chi^2$  tests, together with 95% CIs. Further analyses to allow for potential differences in patient demographics and baseline clinical characteristics between the three diagnostic test groups, and not allowed by stratification, will make use of logistic regression techniques.

*Ventilatory support* The proportions of patients in the three groups who receive ventilatory support within the first 10 days of admission will be compared using  $\chi^2$  tests, together with 95% CIs. Further analyses to allow for potential differences in patient demographics and baseline clinical characteristics between the three diagnostic test groups, and not allowed by stratification, will make use of logistic regression techniques.

Appropriate use of isolation facilities In patients with confirmed influenza or RSV the time taken from admission to the MAU to admission to a single room (isolation cubicle) will be compared between the three diagnostic groups by means of a Log-Rank Test and Kaplan-Meier survival curves. Adjustment for potential differences in patient demographics and baseline clinical characteristics between the three diagnostic test groups, and not allowed by stratification, will make use of Cox proportional hazards regression methods.

*Quality of Life (EQ-5D)* Quality of life in the three diagnostic groups will initially be compared using non-parametric methods. Further analyses to allow for potential differences in patient demographics and baseline clinical characteristics between the three diagnostic test groups, and not allowed by stratification, will make use of generalised linear models in order to accommodate any skewness in the data.

*Speed of Tests* Time taken to receive test results in the three diagnostic groups will initially be compared using non-parametric methods. Further analyses to allow for potential differences in patient demographics and baseline clinical characteristics between the three diagnostic test groups, and not allowed by stratification, will make use of generalised linear models in order to accommodate any skewness in the data.

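### The isolation power of over 95% counts all 2752 patients, but the endpoint covers only influenza or RSV cases, for whom power is about 46%

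*Protocol*

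**What the plan says.** Section 7.4 opens: "Statistical power has been estimated for one laboratory and two clinical endpoints for the elderly population only". Item 3, on isolation, takes the full elderly sample of 2752 and claims that it allows an "improvement in appropriate use of isolation facilities from 5% to 15% to be detected at the 1% significance level with over 95% power". It says that this already allows for 20% dropout and for there being three groups. The synopsis carries the same statement under Statistical power.

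The endpoints use a narrower population. Section 7.5.1 item 4(b), the only isolation endpoint that is a proportion in the patients who should be isolated, reads: "The proportion of patients with influenza or RSV in Groups 1, 2, and 3 who are isolated at any stage during the first 120 hours". Item 4(a), time to a single room, is limited to confirmed influenza or RSV. Item 4(c) concerns inappropriate isolation in *S. pneumoniae* patients. Section 7.6 plans the analysis on the same restricted set: "In patients with confirmed influenza or RSV the time taken from admission to the MAU to admission to a single room". No listed isolation endpoint uses all randomised patients.

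Section 7.1 and the synopsis give the expected case load: 10% of the 2752 with influenza (about 275) and 5% with RSV (about 138), one third in each group.

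**The concern.** The power statement and the endpoint have different denominators. The figure of 2752 is the number recruited, but about 85% of those patients are not expected to enter the isolation comparison. The calculation behind the claim is sound for the number it uses. That number is not the one analysed.

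Isolation is one of two clinical endpoints for which power is claimed, and section 6.2.3 calls its relation to the test results a key measure. If readers accept power above 95%, a non-significant result will look like good evidence that rapid testing does not change isolation. With the cases actually expected, a true tripling from 5% to 15% would be missed more often than it was found.

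**Working it through.** **Inputs.** 2752 elderly patients, rates of 5% and 15%, 1% level, 20% dropout, three groups (section 7.4). Prevalence of 10% influenza plus 5% RSV, equal thirds (section 7.1 and synopsis). Two assumptions are needed because the protocol does not state them: the test is two-sided, and the three-group adjustment is either none, 0.01/2 or 0.01/3.

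**Formula.** Pairwise comparison of two proportions, normal approximation with pooled variance:

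Power = Φ[(0.10 − z·s₀)/s₁], where s₀ = √(2 × 0.10 × 0.90 / n) and s₁ = √((0.05 × 0.95 + 0.15 × 0.85) / n). At two-sided 1%, z = 2.576.

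**Step 1: reproduce the protocol's figure.**
- n = 2752 × 0.8 / 3 = 734 per group, so s₀ = 0.01566 and s₁ = 0.01544.
- Power = Φ[(0.10 − 2.576 × 0.01566) / 0.01544] = Φ(3.86) = 99.99%. At 0.01/3 it is 99.98%.
- So over 95% is met when all patients count.

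**Step 2: use the endpoint's denominator.**
- Cases = 2752 × 0.15 = 413. After dropout, 413 × 0.8 / 3 = 110 per group, so s₀ = 0.04044 and s₁ = 0.03987.
- Power = Φ[(0.10 − 2.576 × 0.04044) / 0.03987] = Φ(−0.10) = 46%.
- This compares about 6 with about 17 isolated patients (110 × 0.05 and 110 × 0.15).

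**Step 3: vary the assumptions (5% v 15%).**

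| Setting | Cases | Level | Power |
|---|---|---|---|
| As step 2 | 110 per group | 0.01 | 46% |
| Adjusted for two comparisons | 110 per group | 0.005 | 37% |
| Adjusted for three comparisons | 110 per group | 0.0033 | 32% |
| One-sided | 110 per group | 0.01 | 56% |
| Conventional 5% level | 110 per group | 0.05 | 70% |
| No dropout | 138 per group | 0.01 | 58% |
| Adding about 57 cases aged 18–64 | 125 per group | 0.01 | 53% |
| Protocol's pooling, less 20% | 227 v 182, × 0.8 | 0.01 | 65% |
| Protocol's pooling, no dropout | 227 v 182 | 0.01 | 77% |

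Unpooled and arcsine versions of step 2 give 47% and 49%. A three-group chi-square test at 1% gives 35% to 59%, depending on the pattern of rates. The most favourable variant tried on the planned case numbers (section 7.1's pooling of 230 v 184, no dropout, one-sided) gives 85%.

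**Step 4: the planned log-rank test.** Risks of 5% and 15% under proportional hazards give a hazard ratio of ln(0.85)/ln(0.95) = 3.17 and about 22 events (110 × 0.05 + 110 × 0.15). Power ≈ Φ(√(22/4) × ln 3.17 − 2.576) = Φ(0.13), about 55%.

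**Step 5: what 95% power would need.** n = [(2.576√0.18 + 1.645√0.175) / 0.10]² = 317.2, so 318 cases per group. At 15% prevalence and 20% dropout this is 3 × 318 / (0.15 × 0.8) = 7950 randomised. At 0.01/3 the figures are 374 per group and 9350 randomised.

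**The case against.** The best defence is that item 3 never says what the 5% and 15% are percentages of. Section 7.3 says evaluations will use both the confirmed cases and all people investigated, and isolation status is recorded for everyone. This allows an all-patient reading in general terms, but no isolation endpoint or analysis is defined that way. Nor are the rates plausible on that reading: 15% of all patients is the entire expected influenza and RSV case load, so every case would have to be isolated. Group 1 has no rapid RSV test, and section 2.2 itself expects more cases than can be isolated.

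Second, the protocol admits that the case numbers are comparatively small and offers pooled rapid and traditional groups for isolation. That is fair, and it raises power to 65% with dropout or 77% without. It does not support the printed figure.

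Third, the case count could be higher. Section 1.2 says at least 10% for influenza and expects molecular tests to find more RSV, and section 7.3 counts any positive test. If 20% to 30% of recruits were positive, unadjusted power would be 61% to 82%. An extreme reading with about 40% positive, many of them falsely, gives about 93%. The protocol does not plan on such numbers, and even that reading falls short of 95%.

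Two smaller points stand. The unadjusted 46% omits the three-group adjustment that the protocol says it makes, so it flatters the design. And restricting Group 1 v Group 3 to influenza (about 73 per group, 29% power) only illustrates the missing RSV test: under intention to treat, those RSV patients stay in and dilute the effect.

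Finally, this is Version 6, dated in the third recruitment season, so the correction adds no patients. That affects what can be done about it, not whether the statement is right.

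**Conclusion.** The concern holds. The stated power of over 95% belongs to a comparison of all recruits that the protocol does not plan. For the population it does plan to compare, power for 5% v 15% at the two-sided 1% level is about 46% unadjusted and about 32% with Bonferroni for three comparisons. It is about 65% for the protocol's own pooled comparison after dropout. These figures rest on the protocol's prevalences of 10% and 5%, its 20% dropout and equal allocation, and on the assumed sidedness and adjustment method. Across the variants of those assumptions that were tried, none reaches 95%. The arithmetic for 734 per group is not at fault; the population is. It must be corrected because it states a property that the design does not have.

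**What to change.** Replace item 3 of section 7.4, and the matching text in the synopsis, with a statement on the analysed population. For example: *About 110 evaluable influenza or RSV patients per group are expected after 20% dropout. For 5% v 15% this gives about 46% power at the two-sided 1% level (70% at 5%) before adjustment for three groups, and about 32% at the 1% level with Bonferroni adjustment for three comparisons. A difference of 5% v 20% has about 79% power at 1% unadjusted and 67% adjusted.* If the pooled rapid v traditional comparison is kept as support, give its power too (about 65% with dropout).

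State the sidedness and the adjustment method, delete the 95% claim, and say that the isolation result will be reported as an estimate with a confidence interval.

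The cost is wording in two places and a less favourable stated figure. It needs no extra patients and no change to endpoints, tests or procedures.

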#### 7.5 Endpoints

Endpoints are divided into clinical, financial, laboratory, and observational.

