#### **RSV positive** Patients will be considered RSV positive if:

The multiplex PCR is positive, and/or

- Viral culture is positive, and/or
- Serology results indicate RSV infection (e.g., ≥4-fold increase in RSV antibodies from Day 1 to Day 30).

S. pneumoniae positive Patients will be considered influenza positive if:

- The Binax NOW S. pneumoniae antigen test is positive, and/or
- Blood culture is positive, and/or
- Sputum culture is positive, AND the sputum sample is macroscopically purulent, AND the sputum sample reveals increased numbers of polymorphonuclear leucocytes, AND the Gram stain is positive, AND there is moderate-to-high amounts of growth, according to criteria used by the laboratory.

Evaluations will be based on: (i) populations whose cardio-pulmonary illness is confirmed as due to influenza, RSV or *S. pneumoniae*, and (ii) the study groups comprising all people who are investigated by the different strategies under investigation (rapid near patient tests, *versus* rapid molecular diagnosis, *versus* conventional laboratory tests).

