#### 7.6 Statistical analysis

All analyses for both process and clinical outcomes will be based on Intention to Treat (ITT) analyses.

Impact of test result on prescribing The time to prescription of `narrow spectrum', `oral antibiotics' or `no antibiotics' between the three groups will be assessed using survival analysis techniques, whilst the use of neuraminidase inhibitors in those with influenza will be assessed using  $\chi^2$  tests, together with 95% CIs. Further analyses to allow for potential differences in patient demographics and baseline clinical characteristics between the three diagnostic test groups, and not allowed by stratification, will make use of cox proportional hazards regression modelling in the case of time to appropriate prescribing and logistic regression techniques in the case of neuraminidase inhibitors.

*Length of hospital stay* Length of hospital stay in the three diagnostic groups will initially be compared using non-parametric methods. Further analyses to allow for potential differences in patient demographics and baseline clinical characteristics between the three diagnostic test groups, and not allowed by stratification, will make use of generalised linear models in order to accommodate any skewness in the data.

*Mortality rates* Mortality rates between the three diagnostic testing groups will be compared by means of a Log-Rank Test and Kaplan-Meier survival curves. Adjustment for potential differences in patient demographics and baseline clinical characteristics between the three diagnostic test groups, and not allowed by stratification, will make use of Cox proportional hazards regression methods.

*Diagnostic accuracy* Sensitivity, specificity, positive predictive value of molecular and near patient diagnostic tests in comparison to traditional laboratory methods will be calculated together with 95% CIs. Heterogeneity in the sensitivity and specificity with respect to patient demographics and baseline clinical characteristics will be explored as secondary analyses using patient defined sub-groups.

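### No primary outcome is named, the comparison is worded in several ways, and the prescribing hypothesis has two different success rules

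*Protocol*

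**What the plan says.** Section 7.5 opens with "Endpoints are divided into clinical, financial, laboratory, and observational" and ranks nothing. Section 7.5.1 has four numbered clinical groups: prescribing (four endpoints), clinical outcomes (six), quality of life (one) and use of isolation (three). Several are wanted both for all patients and for patients with influenza, RSV or pneumococcal infection.

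Section 7.4 states: "Statistical power has been estimated for one laboratory and two clinical endpoints for the elderly population only". The three are diagnostic accuracy, length of stay and appropriate isolation, and no order is given among them. Length of stay is planned for a difference of "1 day in the mean length of stay (assuming SD=6 days", "detected at the 5% significance level with over 80% power", "assuming a 20% dropout rate and adjusting for the fact that there are 3 groups". Isolation is planned for a change "from 5% to 15% to be detected at the 1% significance level with over 95% power", with the same allowances.

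Two bases for evaluation stand side by side. Section 7.3 begins its list with "Evaluations will be based on: (i) populations whose cardio-pulmonary illness is confirmed as due to influenza, RSV" or pneumococcus and then adds the full study groups. Section 7.6 says "All analyses for both process and clinical outcomes will be based on Intention to Treat (ITT) analyses". Neither section says which basis decides.

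The comparison is worded in three ways:
- Groups 1 and 2 against Group 3: synopsis (assessment methods) and several items of 7.5.1.
- The three groups compared together: section 7.6.
- Pooled rapid against pooled traditional viral cases, as something that may be done: section 7.1.

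The prescribing hypothesis covers earlier narrow-spectrum therapy, earlier oral switch and earlier stopping. Hypothesis 3 of the synopsis joins these with 'and'; section 2.1, item 3, joins them with 'and/or'.

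**The concern.** The candidate outcomes can disagree. Stay could shorten with no change in prescribing, or a pathogen subset could show an effect that all patients do not. The protocol has no rule for what the trial concludes in those cases. A report could follow the text faithfully and rest its conclusion on any of many unranked results. Under the section 2.1 wording, one of three prescribing results is enough.

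This is more than a missing analysis detail. The choice of outcome and contrast determines the sample size, and section 7.4 already claims power at stated significance levels. It is a protocol decision even where a separate analysis plan exists.

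**Working it through.** **1. The plan's own length-of-stay figure.** Inputs from 7.4: 2752 patients, 20% dropout, three groups, difference 1 day, SD 6. Equal allocation and two-sided tests are assumed.

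- Per group: 2752 × 0.8 / 3 = 733.9.
- Standard error: 6 × √(2/733.9) = 0.3132, so the expected z is 1/0.3132 = 3.19.
- Power ≈ Φ(3.19 − critical value).

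| Adjustment | Critical value | Power |
|---|---|---|
| None (5%) | 1.96 | 89.1% |
| Two contrasts with Group 3, Dunnett | 2.21 | 83.7% |
| Two contrasts with Group 3, Bonferroni (2.5%) | 2.24 | 82.9% |
| All three pairs, Bonferroni (1.67%) | 2.39 | 78.8% |

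The stated power of over 80% is reproduced for two contrasts against Group 3. It is just missed for all pairs under Bonferroni, so the choice of contrasts matters to the plan's own claim.

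**2. Chance of a false favourable result if nothing is ranked.** Assumptions: no true effect, each test at |z| > 1.96, Groups 1 and 2 each against Group 3 (contrasts correlated 0.5 through the shared group), equal correlation ρ between endpoints. The protocol gives no value for ρ, so a range is shown.

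One endpoint with two contrasts gives 9.1% in either direction, so about 0.091/2 = 0.0455 favourable. For k independent endpoints the chance is 1 − (1 − 0.0455)^k; for ρ > 0 it was simulated with 200,000 runs.

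| Endpoints | ρ = 0 | ρ = 0.5 | ρ = 0.8 |
|---|---|---|---|
| 3 (time-to-event prescribing, 1(a) to 1(c)) | 13% | 11% | 9% |
| 10 families | 37% | 24% | 15% |

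The ten families are prescribing, stay, fever, oxygen, CPAP, intensive care, ventilation, death, quality of life and isolation, with one test each.

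If each endpoint were held at 5% across its two contrasts, its favourable error would be about 2.5%. Ten independent endpoints would then give 1 − 0.975^10 = 22.4%, and less with correlation.

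**3. Correcting for everything instead.** Bonferroni over 10 endpoints × 2 contrasts (0.05/20 per test) cuts length-of-stay power to 56.7%.

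**4. Isolation as an alternative.** Section 7.4 states its power for 2752 patients, and with all of them it exceeds 99.9% at the 1% level. But endpoints 4(a) and 4(b) are limited to influenza or RSV cases. With the 10% and 5% expected in 7.1, the number per group is 2752 × 0.15 × 0.8 / 3 = 110. For 5% against 15%:

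- Standard error under the null: √(2 × 0.10 × 0.90/110.08) = 0.0404.
- Standard error under the alternative: √((0.05 × 0.95 + 0.15 × 0.85)/110.08) = 0.0399.
- Power at 1%: Φ((0.10 − 2.576 × 0.0404)/0.0399) = 46%.
- After a three-group adjustment: 37% at 0.5% (two contrasts) and 32% at 0.33% (three pairs).

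**The case against.** The strongest reply is that rules across endpoints, such as testing order and alpha allocation, commonly sit in an analysis plan, and none is shown here. That stands, and their absence is not the point. The choice of primary outcome is different and belongs in the protocol. Nothing in this one substitutes for it: section 1.11 calls technology assessment the main driver, which is an aim, and section 7.5.2 names two main measures for the economic evaluation only.

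A reader might go further and infer that ten endpoint families all carry benefit hypotheses at full alpha, so that a false claim that rapid testing works is likely. The document does not support this:

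- Both clinical power statements adjust for three groups, and isolation is set at 1%. Section 7.6 states no significance level.
- Section 2.1 attaches benefit hypotheses to prescribing, isolation and quality of life, with earlier discharge as a route to savings and better quality of life. Fever, oxygen, CPAP, intensive care, ventilation and death fall under a hypothesis of no harm.
- Section 7.6 describes no test for fever, oxygen or CPAP duration, nor for isolation endpoints 4(b) and 4(c).
- Groups 1 and 2 against Group 3 is written in the synopsis. The comparison is therefore worded inconsistently, not left unnamed. The three-group wording of 7.6 could also mean one overall test per endpoint.
- Counting significance in either direction gives 29% to 61% for ten families, but that includes results against rapid testing. The favourable share is 15% to 37%, below even odds.

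These points limit the size of the problem and leave the central gap in place.

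**Conclusion.** The point holds in this form: no primary outcome is named, three endpoints with power or precision statements are unranked, the comparison is worded inconsistently, and the prescribing hypothesis has two incompatible success rules. The chance of at least one false favourable result is 15% to 37% across ten families and 9% to 13% for the three time-to-event prescribing endpoints, against 2.5% for a single two-sided 5% test.

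These figures rest on one test per family, two contrasts at unadjusted 5% and an assumed correlation of 0.8 to 0. They show what the text permits; they do not predict what the analysts would do. Applying the section 7.4 group adjustment to every test lowers them but does not control error across endpoints.

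**What to change.** In 7.5, name one primary outcome, its population and its contrasts, and use the same contrast wording in the synopsis, 7.1, 7.5.1 and 7.6.

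Length of stay in all patients, with Group 1 against 3 and Group 2 against 3 at a family-wise error of 5%, is the natural candidate. It is a powered clinical endpoint and is defined first for all patients. Section 7.4 powers it for the elderly only, so the population statement should say how the 18 to 64 age group is handled. The final choice is the investigators'.

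Label the other endpoints and the pathogen subsets as secondary or exploratory. Reconcile 'and' in the synopsis with 'and/or' in 2.1 by naming one prescribing endpoint. Do not present isolation in confirmed influenza or RSV cases as a powered key secondary, given about 46% power at 1%.

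The cost is wording only. No patients are added: two Bonferroni contrasts at 80% power need 2569 patients including dropout, within the planned 2752. The downside is that fewer results can be called confirmatory.
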